9 STATISTICAL CONSIDERATIONS

9.1 General Design Issues

The primary hypothesis for the **ISTEP** study is that pharmacist-led immunosuppressant therapy management, facilitated through the use of innovative technology, will significantly improve immunosuppressant safety and clinical outcomes in Veteran transplant recipients.

The study will consist of a 24-month prospective, parallel arm, cluster-randomized, controlled multicenter study. The clinical trial will randomize 10 sites, 5 to standard of care and 5 to standard of care plus the below-discussed intervention, using prospective methodology to monitor patients for 24-months following site-randomization, comparing outcomes between the treatment and control sites. The cluster-randomized design of this study was chosen for a number of important reasons. First, this study design will allow investigators to test a promising intervention against a similar control group with respect to patient constitution and time. The use of randomization at the site level will allow us to complete the 24-month study within a reasonable period and within the budget constraints. Using the cluster randomized parallel design at 10 sites will provide sufficient patient numbers to meet statistical power to detect clinically meaningful differences in health care utilization. Randomization at the patient-level, as opposed to the site, would not be feasible, as there would be a high probability of cross-contamination based on the intervention proposed and the technology component, which uses site-specific population surveillance. Additionally, randomization at the patient-level would substantially prolong enrollment, thus making completion within 4 years infeasible. Other trial designs were considered and discussed with the investigational group, including stepped-wedge, interrupted time series, one group pre-post test, one group post-test only and a traditional patient-level randomization. The stepped wedge is the best alternative to our proposed study, but would provide limited time to evaluate outcomes at some of the sites. Given the proposed intervention type, the use of population-surveillance technology, the number of sites recruited and the time and budget constraints, the investigative team felt that the parallel-group, cluster randomized controlled trial was the strongest in terms of methodology, internal validity, statistical power, feasibility, and likelihood of success.

There are three main hypotheses this study aims to test:

1. Veterans in the intervention group will have significantly lower rates of hospitalizations and emergency room visits, as compared to the control group, at the end of the 24-month study.
2. Veterans in the intervention group will have significantly reduced health care costs, as compared to the control group, at the end of the 24-month study.
3. The immunosuppressant dashboard system will provide near real-time, actionable alerts that will allow the pharmacist to conduct timely interventions on potential or ongoing drug-related problems.

9.2 Sample Size and Randomization

Based on the projected enrollment numbers, there is ample power to detect a statistically significant difference between the intervention and control groups with regards to the primary aim of hospitalization and ED visit rates. To determine this, we used data from a recent national study conducted between 2009-2012.⁵³ These results demonstrated that the rate of ED visits after transplant was 1.269 per person-year and 48% of those ED visits resulted in hospitalization. We will enroll 10 sites (5 sites for each study arm) and will have a total of just more than 1,600 patients that are roughly split between the intervention and control sites. We used a conservative estimate of an intra-cluster correlation of 0.05 and calculated a sample size of 1,350 to allow us to detect a 25% relative decrease in ED visit and hospitalization rates with 80% power. The 25% relative improvement in rates is a conservative estimate of intervention effect, based on previous pharmacist-led initiatives the investigators have conducted.^{15,16} After allowing for 15% loss to follow up, we require a total of 1,600 to meet study power. We expect to have 1,689 patients based on site estimates. These power calculations were conducted using a two-sided test for counts with Poisson regression adjusting for intra-cluster correlation and with alpha set at 0.05.

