9.3.1 Primary outcome

The primary outcome for this study will include the overall rate of ER visits and hospitalizations, compared between the intervention and control groups. These encounters will be captured electronically throughout the 24-month study through the use of the CDW, stored in the VINCI environment. In addition, to ensure encounters are captured in a comprehensive manner, we will also link the VA CDW data to CMS (Medicare) claims data and capture non-VA ER and hospitalization encounters (after study completion). As most transplant patients are dual users and have Medicare

insurance benefits, this linkage will provide a more accurate assessment of these health care utilization.³ We expect ER visits and hospitalizations to significantly decrease within the intervention arm, towards the latter half (second 12-months) of the study due to a lag effect of the intervention on this outcome. This expectation is based on our previous research in this field and assessment of pharmacist interventions on medication safety and reduced adverse drug events requiring hospitalization. ER visits and hospitalizations will be assessed and compared as described in the statistical analysis plan. These will be defined based on encounter criteria within the CDW and CMS data: all-cause ER visits and all-cause hospitalizations leading to at least one overnight stay will be included as events.

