9.4 Data Analyses

The data analysis will incorporate the intent-to-treat principle; namely, all participants enrolled in the intervention group will be included in the analysis and compared to all of the patients captured within the control group. If a patient dies, has graft loss or moves out of their study site, their data will be censored at that time point. For comparative statistical assessments within the utilization outcomes, the two groups will be compared using a generalized linear mixed models (GLMM) approach.⁵⁴ This approach allows for measurement of participants at different time points, clustering by study site, missing data under the assumption of missing at random (MAR), time varying or invariant covariates, and can also account for the effect of correlated longitudinal measurements within participants. In addition, GLMM accommodates a wide range of distributional assumptions such as dichotomous (e.g. binomial), count (e.g. Poisson), continuous

(e.g. Gaussian), and categorical or ordinal outcomes. For comparing the primary outcome (ED visit and hospitalization rates), we will use GLMM (with appropriate link function) with counts of these events as the outcome variable and intervention group (yes/no) as the primary independent variable. This analysis is equivalent to Poisson regression or negative binomial regression (in the case of over-dispersion), both special cases of GLMM. Additional adjustment covariables will be added to the model in a second set of analyses. Covariates will include patient sociodemographics: age, sex, race, comorbidities (using modified Elixhauser definitions), marital status and education. In these models, donor information (age, sex, race, deceased or living) and transplant characteristics (HLA mismatches, ischemic times, panel reactive antibody levels, time since transplant) will also be included. This will assist in making valid intervention effect estimates after accounting for baseline differences, as there may be patient-level differences between groups. The magnitude of between intervention differences on outcome variables (effect sizes) at each time point will be estimated using appropriate contrasts in the corresponding GLMM models.

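### On the inputs that reproduce the 1,350 sample size, power for a 25% reduction is about 70%, not 80%, once the test uses the 8 degrees of freedom that 10 sites allow; section 9.4 names no small-sample method

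*Combined protocol and SAP*

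**What the plan says.** Section 9.2 sizes the trial from an external national study in which "the rate of ED visits after transplant was 1.269 per person-year and 48% of those ED visits resulted in hospitalization". It takes an ICC of 0.05 and 10 sites, five per arm, and states that the investigators "calculated a sample size of 1,350 to allow us to detect a 25% relative decrease in ED visit and hospitalization rates with 80% power". On method it says only: "These power calculations were conducted using a two-sided test for counts with Poisson regression adjusting for intra-cluster correlation and with alpha set at 0.05". After a 15% allowance for loss to follow-up it concludes that "we require a total of 1,600 to meet study power", expects 1,689 patients, and calls the power ample. Section 9.1 repeats the assurance: "Using the cluster randomized parallel design at 10 sites will provide sufficient patient numbers to meet statistical power".

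Section 9.3.1 defines the endpoint more widely than ED visits: "all-cause ER visits and all-cause hospitalizations leading to at least one overnight stay will be included as events".

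For the primary comparison section 9.4 says "we will use GLMM (with appropriate link function) with counts of these events as the outcome variable", and adds: "This analysis is equivalent to Poisson regression or negative binomial regression (in the case of over-dispersion), both special cases of GLMM". It lets AIC and BIC choose among Poisson, negative binomial and zero-inflated forms. It gives no denominator degrees of freedom, small-sample correction, site-level test or permutation test.

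**The concern.** With an ICC of 0.05 and well over 100 patients per site, most of the variance of the treatment effect comes from differences between sites. Only 10 sites estimate that variance, so the treatment test has 10 − 2 = 8 degrees of freedom, however many patients each site contributes. A calculation with normal quantiles treats the between-site variance as known and overstates power.

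80% is the only power figure in the plan. If it depends on a normal reference, the sponsor faces a choice that the text does not show. The test can hold alpha at 0.05 with power well below 80%, or keep 1.96 and the 80% with an inflated type I error. Because section 9.4 is silent, the choice would fall to the analyst, possibly after the data are in.

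**Working it through.** **Inputs.** From section 9.2: control rate 1.269 ED visits per person-year, rate ratio 0.75, ICC 0.05, two-sided alpha 0.05, 80% power, five sites per arm. Exposure is taken as the trial's 24 months; section 9.2 does not state it. Patients per site: 1,350/10 = 135. Design effect: 1 + (135 − 1) × 0.05 = 7.7.

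**1. Reproduce 1,350.** Expected counts per patient are 1.269 × 2 = 2.538 and 0.75 × 2.538 = 1.9035, a difference of 0.6345.

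- Difference scale: n per arm = (1.96 + 0.8416)² × (2.538 + 1.9035)/0.6345² = 86.6, and 86.6 × 7.7 × 2 gives N ≈ 1,334.
- Log scale: n per arm = (1.96 + 0.8416)² × (1/2.538 + 1/1.9035)/(ln 0.75)² = 87.2, so N = 1,343.
- Loss to follow-up: 1,350/0.85 = 1,588, rounded up in the plan to 1,600.

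Other readings with the same method miss clearly. ED visits over one year need about 2,670. Hospitalizations alone over two years need about 2,780. ED visits plus hospitalizations (1.269 × 1.48 = 1.878 per person-year) need about 900 over two years or 1,800 over one.

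**2. Power at 1,350.** Noncentrality = 0.6345/√(4.4415 × 7.7/675) = 2.819.

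- Normal reference (1.96): 80.5%.
- Noncentral t on 8 df (2.306): 69.6%.
- Log scale (noncentrality 2.809): 80.2% and 69.3%.

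**3. More patients in the same 10 sites** (difference scale).

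| Patients per site | Noncentrality | Power, t on 8 df |
|---|---|---|
| 135 (N = 1,350) | 2.819 | 69.6% |
| 168.9 (N = 1,689) | 2.854 | 70.6% |
| Unlimited | 3.011 | 75.1% |

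Power of 80% on 8 df needs a noncentrality of 3.20, so no number of patients reaches it at ICC 0.05.

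**4. Keeping 1.96.** On a statistic with 8 df this gives power of 79.6% (135 per site) to 80.5% (169), but a type I error of 2 × P(t₈ > 1.96) = 8.6%. Simulation of a site-level test gave 8.5% to 8.6%.

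**5. What reaches 80% on 8 df.** A reduction of 28.1% (135 per site) or 27.8% (169); or, for a 25% reduction, an ICC of 0.0371 or 0.0385 respectively. Across ICCs, for 135 to 169 per site:

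| ICC | Power, t on 8 df |
|---|---|
| 0.03 | 86–88% |
| 0.037 | 80–81% |
| 0.05 | 70–71% |
| 0.08 | 52–53% |

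**6. Sensitivity.**

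- Size stratum in the model (7 df): about 68% at 135 per site, 69% at 169.
- ICC read as a constant site coefficient of variation, √(0.0526/2.538) = 0.144, where 0.0526 = 0.05/0.95. Simulated site-level test on 8 df: 72–73% at 135, 73.5–74% at 169, about 79% with very large sites.
- Site variance proportional to the arm mean, simulated: 67.6% at 135.
- Summed rate, 1.878 × 2 = 3.756 events, ICC held at 0.05: 85–86%. This implies a smaller site coefficient of variation, √(0.0526/3.756) = 0.118. With 0.144 kept, about 74–76%.
- Over-dispersion, illustration only: assumed negative binomial dispersion of 0.5 to 1.0, with the between-site variance unchanged, gives 64% to 59% at 135 and 66% to 61% at 169.

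**The case against.** The strongest reply is that the inputs are inferred. Section 9.2 does not state the exposure, which rate entered the formula, or the reference distribution. A rival set also returns 80% at 1,350 on 8 df: the summed rate with a mean exposure of about 1.745 years. Rolling entry and exit (section 4.2) and censoring at death, graft loss or moving (section 9.4) make a mean below 24 months possible. For the endpoint as section 9.3.1 words it, summed counts at ICC 0.05 over a full 24 months give 85–86% on 8 df. The plan also calls its ICC conservative, and 0.037 would restore 80%. Finally, the plan never says it will use 1.96, and the type I error above comes from a site-level statistic; the mixed model itself was not simulated.

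Part of this stands. The 70% is conditional on the reconstructed inputs, and section 9.2 needs to state its own. Whether an ED visit ending in admission counts once or twice is also unsettled. But the rival set needs an exposure that appears nowhere in the documents and is tuned to the answer, whereas the ED-only, 24-month, normal-quantile calculation uses the documents' own figures and lands within about 1% of 1,350. The summed rate over 24 months would have needed only about 900 patients, so it is not the calculation reported. The silence in section 9.4 is not disputed.

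**Conclusion.** The concern holds. On the inputs that produce 1,350, the stated 80% power and 5% alpha cannot both be true. Holding alpha gives about 70% power, so the chance of missing a true 25% reduction is about 30% instead of 20%. The number of sites sets this limit, and recruiting 1,600 or 1,689 patients does not lift it.

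This rests on ED visits alone at 1.269 per person-year, 24 months of exposure for every patient, equal site sizes, Poisson variance and ICC 0.05. Other readings of the ICC move the ED-only figure within about 67% to 74%. Over-dispersion, which section 9.4 anticipates, would lower it; a smaller ICC, or a summed rate with the ICC held at 0.05, would raise it.

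**What to change.** In section 9.2:

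1. State the event rate, exposure and reference distribution behind 1,350. The reconstruction points to ED visits only, 24 months and normal quantiles; if so, say so, because section 9.3.1 counts hospitalizations too.
2. Restate power with a t reference on 8 df: about 70% for a 25% reduction, or 80% for about 28%, at 10 sites, ICC 0.05 and 1,350 to 1,689 patients.
3. Show the ICC range tabled above and, labelled as assumed, a range over negative binomial dispersion.
4. Remove the description of power as ample and the statement that 1,600 patients meet it. Align the matching sentence in section 9.1.

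In section 9.4, add one sentence: whichever count model is selected, the treatment effect is tested with between-site denominator degrees of freedom (10 sites minus 2 arms = 8) or a named small-sample correction. If the size stratum from section 9.2.1 enters the model, use 7, and base the restated power on the same number.

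The cost is rewording only, with no extra sites or patients. The stated power becomes less favourable: the t reference gives up about 10 points against 1.96 in return for a 5% type I error.

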We anticipate that some of the count outcomes will exhibit excess zeros (e.g. hospitalizations). If the counts exhibit excess zeros, we will use zero-inflated (ZI) versions of the proposed model (zero inflated Poisson and zero-inflated negative binomial [NB]) to account for the excess zeros with random effects to account for clustering by site.⁵⁵ Typically, Poisson regression is used to model count data where observations are assumed to be independent and the number of cases has variance equal to the mean for each level of the covariates. However, in practice, either the independence or equal mean and variance assumption is often violated, which can lead to over-dispersion (when the variance is greater than the conditional mean). Thus, we consider a NB model that handles the problem of over-dispersion and that does not assume an equal mean and variance assumption. In certain cases, over-dispersion may not be sufficiently modeled via the extra parameter in NB. In this case we will consider including random effects into the NB model. Zero inflated models such as ZINB can be used for modeling the excess zeros. The ZINB model is a mixture of NB model for the count part and a logit model for the excess zeros. The parameters in the ZINB model have conditional or latent class interpretations, which correspond to a susceptible subpopulation at risk for the condition (in our case ED visits/hospitalizations) with counts generated from a NB distribution and a non-susceptible subpopulation that provides the extra or excess zeros. Thus, the ZINB model parameters are not well suited for quantifying the effect of an explanatory variable in the overall mixture population. We will use a marginalized ZINB model to estimate the population mean count directly, allowing straightforward inference for overall covariate effects.⁵⁶ We will use AIC and BIC, which deal with the trade-off between the goodness of fit and complexity of the models, to choose the best fitting model among the different models; further assessment of the goodness of fit for the final model is made via the Pearson goodness of fit statistic. A model with a smaller value of AIC, BIC, and a Pearson statistic close to one is considered a better fit of the data. We will use SAS 9.4, housed within the VINCI environment, to manage the data and fit all the models.

For the cost analysis, we will also utilize multivariable modelling and propensity score

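### The 80% power in section 9.2 assumes pure Poisson counts, with no allowance for the patient-level over-dispersion that section 9.4 provides for; on the plan's own inputs it is a best case

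*Combined protocol and SAP*

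**What the plan says.** Section 9.2 takes its event rate from a national study: the "rate of ED visits after transplant was 1.269 per person-year and 48% of those ED visits resulted in hospitalization". With an ICC of 0.05, which it calls conservative, and five sites per arm, it arrives at 1,350 patients to "detect a 25% relative decrease in ED visit and hospitalization rates with 80% power". It raises this to 1,600 for 15% loss and expects 1,689. The method is given as a "two-sided test for counts with Poisson regression adjusting for intra-cluster correlation and with alpha set at 0.05". The section describes the power as ample and states neither a dispersion parameter nor a zero fraction.

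Section 9.3.1 defines the primary outcome as all-cause ER visits together with all-cause hospitalizations that include an overnight stay.

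Section 9.4 describes the primary model as equivalent to "Poisson regression or negative binomial regression (in the case of over-dispersion"). On the distribution it says "We anticipate that some of the count outcomes will exhibit excess zeros (e.g. hospitalizations"), and that "in practice, either the independence or equal mean and variance assumption is often violated, which can lead to over-dispersion". It then provides negative binomial (NB), zero-inflated and marginalized zero-inflated NB models, and applies the idea of susceptible and non-susceptible subpopulations to ED visits and hospitalizations.

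**The concern.** The two sections work from different variances. The design effect in 9.2 covers the similarity of patients at the same site. It does not cover patients within a site differing from one another, such as frequent users and people who never attend. Under a Poisson count with mean 2.538, exp(-2.538) = 7.9% of controls would have no event in two years. Section 9.4 prepares for distributions with more zeros and a larger variance than that, but nothing is carried back into the sample size.

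What is at stake is how a non-significant result is read. If counts are over-dispersed and power is quoted as 80%, a null result would be taken as stronger evidence against a 25% reduction than the trial could supply.

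**Working it through.** **Inputs from section 9.2.** ED rate 1.269 per person-year; rate ratio 0.75; ICC 0.05; 10 sites, 5 per arm; N = 1,350, so 675 per arm and 135 per site; two-sided alpha 0.05. Follow-up is 24 months (section 9.1). A normal reference is used, and every patient is taken to contribute the full 24 months, because the plan's figure reproduces on that basis.

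**Reproducing the plan.**
- Means: mu0 = 2 x 1.269 = 2.538; mu1 = 0.75 x 2.538 = 1.9035.
- Design effect: 1 + (135 - 1) x 0.05 = 7.7.
- Per arm before clustering: (1.960 + 0.842)^2 x (1/2.538 + 1/1.9035) / (ln 0.75)^2 = 87.2.
- Total: 2 x 87.2 x 7.7 = 1,343, against 1,350 stated.
- Power at 1,350: Var(log RR) = 7.7 x 0.9194 / 675 = 0.01049, SE = 0.1024, power = Phi(0.2877/0.1024 - 1.96) = 80.2%.
- Loss allowance: 1,350/0.85 = 1,588, close to the stated 1,600.

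**Adding patient-level dispersion.** For an NB count the variance is mu(1 + k mu), so 1/mu becomes 1/mu + k per patient. The documents give no k; 0.25 to 1 is an assumed range. They also do not say which variance the ICC of 0.05 refers to, so there are two cases.

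(i) *Site variance held at its Poisson level*, so that only patient heterogeneity is added: Var = sum over arms of [0.95(1/mu + k) + 0.05 x 135/mu] / 675. At k = 0.5 this is 0.01189, SE 0.1091.

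(ii) *ICC 0.05 applied to the over-dispersed variance*: Var = 7.7 x sum over arms of (1/mu + k) / 675. At k = 0.5 this is 0.02189, SE 0.1480. Here the between-site variance also grows by the factor 1 + k mu0 in the control arm: 2.3-fold at k = 0.5 and 3.5-fold at k = 1.

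| k (assumed) | Controls with no event | Power, case (i) | Power, case (ii) |
|---|---|---|---|
| 0 | 7.9% | 80.2% | 80.2% |
| 0.25 | 14% | 78% | 62% |
| 0.5 | 19% | 75% | 49% |
| 1 | 28% | 70% | 35% |

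The reduction detectable with 80% power at k = 0.5 is about 26% in case (i) and 34% in case (ii), against 25% stated. Power at 1,350 falls to exactly 80% at k of about 0.02 in case (i) and 0.002 in case (ii), so the stated figure has essentially no margin.

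**Surplus enrolment.** With all 1,689 patients and no losses, Poisson power is 81.2%, because the number of sites is fixed. At k = 0.5 it is 77% in case (i) and 50% in case (ii).

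**Counting rule.** If an ED visit and the admission that follows it are counted as two events, mu0 = 2.538 x 1.48 = 3.756. At N = 1,350 Poisson power is then 93%. In case (i) it is 90%, 88% and 82% at k = 0.25, 0.5 and 1. In case (ii) it is 72%, 56% and 38%, crossing 80% at k of about 0.15. The same formula with this mean gives N = 907.

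**The case against.** **Is power actually below 80%?** A reader might infer that the primary analysis has less power than stated. The documents do not establish that. The primary outcome includes hospitalizations, and the mean of 2.538 is ED visits only. With both counted, power stays above 80% to about k = 1 when site variance is held. This stands as a limit on the conclusion. It does not rescue 9.2, because a mean of 3.756 implies 907 patients and so is not the basis of the 1,350.

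**Are 62%, 49% and 35% the effect of patient heterogeneity?** No. Those figures also enlarge between-site variance, and nothing in the documents says sites differ that much. Patient heterogeneity alone gives 78%, 75% and 70%. The lower figures apply only if the ICC was defined on over-dispersed counts, which the plan leaves open.

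**The ICC is called conservative.** At an assumed ICC of 0.04 with site variance held, power is 84% at k = 0.25 and 82% at k = 0.5; with the ICC applied to the over-dispersed variance it is 70% and 57%. The result is thus sensitive to the ICC as well as to k. But the plan quantifies no margin in its 0.05.

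**Section 9.4 is partly conditional.** It anticipates excess zeros outright, but for some counts, with hospitalizations as the example. Over-dispersion is treated as something that may arise. To say the plan expects it in the ED count would go beyond the text.

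**The analysis already handles over-dispersion.** The planned models protect the validity of the test and its interval. They do not restore power.

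**Conclusion.** The point holds as an inconsistency between a design assumption and the analysis plan. It is not an arithmetic error: the stated sample size reproduces. On the plan's own inputs, 80% power is what the trial has if patients do not differ in their underlying event rate, and calling that ample is unsupported.

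The direction is firm: for any given mean and ICC, over-dispersion lowers power relative to the Poisson figure. The size is not firm. For the ED-visit mean that underlies the 1,350, patient heterogeneity alone costs about 2 to 10 percentage points over k = 0.25 to 1. A much larger loss requires the second reading of the ICC. All of these figures rest on an assumed k, a normal reference and full 24-month follow-up. They do not support a claim that the trial is severely underpowered, or that its true power must be below 80%.

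**What to change.** In section 9.2:
- Replace the Poisson variance with the NB variance (1/mu + k per patient in each arm).
- State whether the ICC of 0.05 refers to the Poisson or the over-dispersed variance.
- State which events the assumed mean counts.
- Restate power, or the reduction detectable with 80% power, at 10 sites over a range of k.
- Label 80% as the no-over-dispersion case and remove the description of power as ample.

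Inform k and the between-site variance from pre-study 24-month CDW counts of ED visits and hospitalizations at the participating sites; the cost analysis already draws on the two years before the study. Note beside the result that these counts are VA-only, because section 9.3.1 links CMS encounters after study completion, so they approximate the primary outcome rather than match it.

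The cost is one data query and a rewritten paragraph. The stated power becomes less favourable. No sites, patients or procedures change.
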